CooperVision™

FINAL

Performance of Two Toric Silicone Hydrogel Contact Lenses

Sponsor Study Code: EX-MKTG-128

Protocol Date: August, 2021

Sponsor Company: CooperVision, Inc.

Document Type: Protocol

Study Category: Post Market

Start Date: September 2021

Finish Date: December 2021

[figure not shown]
Clinical Site: [name] [name]
National Autonomous University of México. [name]

Revision History

Document number	Date	Comments
EX-MKTG-128	08/16/2021	First draft (v 1.0)
EX-MKTG-128	08/18/2021	Second draft (v 2.0)
EX-MKTG-128	08/19/2021	FINAL

Confidential

1

[figure not shown]
[figure not shown]

Protocol Synopsis

Protocol Number	EX-MKTG-128
Title	Performance of Two Toric Silicone Hydrogel Contact Lenses
Name of Device(s) and (by USAN material)	Miru 1 month Menicon toric lens (Asmofilcon A), Avaira Vitality™ toric (fanfilcon A)
Indications for Use	
Approved for use:
 
 • Asmofilcon A. (Daily wear) • fanfilcon A. (Daily wear) 
Indication for use in this study:
 
 • 1 month of daily wear
Study Design	Single-site, prospective, randomized, double masked, cross-over, 1-month daily wear study. This study will evaluate the Avaira Vitality™ toric when compared to the Miru 1month Menicon toric lens after 1-month of daily wear.
Purpose	Evaluate the clinical performance and subjective acceptance of two toric silicone hydrogel contact lenses after 1-month of daily wear.
Study Duration	
The anticipated timeline for this study is as follows:
 
 • Patient enrolment and completion: Sept 20th - Nov 30th, 2021 • Visits: V1: (BL/trial fit/lens order), V2: (Dispense P1), V3: (2-week visit P1), V4: (1-month visit P1/dispense P2), V5: (2-week visit P2), V6: (1-month visit P2/study exit).
Patient Population	Adapted soft contact lens wearers with astigmatism that provide written informed consent and meet protocol entry criteria.
Sample Size	Target enrollment is 38 subjects and completion of 33 in total .
Center Destination (Mexico)	National Autonomous University of Mexico. [name].
Number of Centers	Single-Center

The utilization of soft toric contact lenses has increased significantly over the past few years. Toric contact lens wearers demand two things from their contact lenses, great comfort, and excellent vision. CooperVision's Avaira Vitality™ toric uses a third generation silicone hydrogel material which makes the lens inherently wettable with no surface treatments and uses naturally wettable building blocks to improve compatibility between silicone and hydrophilic domains. This combined with the higher water content of Avaira Vitality™ toric ensures a high performing, comfortable lens.

Menicon recently launched its Miru 1month lens family in the U.S. market, a monthly replacement silicone hydrogel lens in spherical, toric, and multifocal designs. Miru 1month toric Menicon is a monthly replacement silicone hydrogel contact lens manufactured in asmoofilcon A material that has a water content of 40%. It uses both MeniSilk and NanoGloss technologies. The Miru 1month toric Menicon uses a unique double vertical asymmetric Thin Zones called Visiostable design™. The unique asymmetric vertical Thin Zones matches the eyelids natural asymmetric coverage of the cornea, harnessing the natural lid force, optimizing centration, and preventing rotation. A lens designed to work with the eyes for clear, comfortable vision

Therefore, CooperVision is interested in evaluating the clinical performance of the Avaira Vitality™ toric and Miru 1month toric Menicon lenses when existing wearers of hydrogel toric lenses are refitted with these lenses over 1 month of wear.

2 Study Objective

The aim of this prospective study is to evaluate the clinical performance and subjective acceptance of two toric silicone hydrogel contact lenses after 1-month of daily wear.

Primary outcome variable:

- Lens handling ratings (ease of insertion & removal. 0 -10 scale)

- [REDACTED]
- [REDACTED]
- [REDACTED]
- [REDACTED]

3 Study Hypothesis

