3.1 Study Hypothesis

- Null hypothesis (Ho): There is no difference between the Avaira Vitality™ toric and Miru 1month toric Menicon lenses in subjective lens handling ratings.
- Alternative hypothesis (H1): There is a difference between the Avaira Vitality™ toric and Miru 1month toric Menicon lenses in subjective lens handling ratings.

4 Study Design

This is a 38-subject, prospective, randomized, double masked, (investigator and participant), bilateral, 1 month cross-over study comparing the handling characteristics, (insertion & removal), of asofilcon A toric lenses against fanfilcon A silicone hydrogel toric lenses (table 1). It is anticipated that this study will involve up to 6 scheduled visits: At the first visit, (V1), subject's habitual toric lenses will be evaluated and then re-fitted with both study lenses [REDACTED]. At the second visit, (V2), the first pair of study lenses, (e.g., asofilcon A or fanfilcon A toric lenses), will be dispensed. After 2 -weeks of daily wear, subjects will return for a third evaluation, (V3), and a 4-week visit will be scheduled. At the 4-week visit, (V4), pair 1 will be evaluated and then pair 2 dispensed. Next, a 2-week, (V5), and 4-week visits, (V6) will be scheduled. At visit 6, subjects will exit the study. [REDACTED]

5 Investigational Sites

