If eligible, complete the Enrolment Log and identify the test lens [REDACTED]. The subjects will undergo a trial fit in both eyes with both study lenses (e.g., Avaira Vitality Toric and Miru 1month Menicon toric, according to manufacturer’s fitting guides) to ensure optimization of the lens parameters needed to provide the best distance visual acuity. Re-order final lens if appropriate. If the lenses are not suitable to be dispensed, then the subject will be discontinued and an Exit form will be completed.

8.3.2 Visit 2: Dispense pair 1

- Data is only collected on the final pair of study lenses dispensed after the power has been assessed and if needed corrected.

- Record the parameters of the lenses, [REDACTED] on the Dispensing CRF [REDACTED]
- [REDACTED]
 - [REDACTED]
 - [REDACTED]
 - [REDACTED]
 - [REDACTED]
 - [REDACTED]
 - [REDACTED]
 - [REDACTED]
- [REDACTED]
 - [REDACTED]
 - [REDACTED]
- [REDACTED]
 - [REDACTED]
 - [REDACTED]
 - [REDACTED]
 - [REDACTED]
 - [REDACTED]
 - [REDACTED]
 - [REDACTED]
 - [REDACTED]
 - [REDACTED]
- [REDACTED]
 - [REDACTED]
- Lost or damaged study lenses may be replaced. Note which lens was replaced, date of replacement and reason for replacement on the Lens Replacement Log, [REDACTED]
- The subject will be instructed to wear the lenses on a daily wear basis, (at least 40 hours per week), until the 2-weeks follow-up appointment, unless they experience a problem which warrants lens removal.
- The Investigator or a clinical assistant will review instructions and warnings for lens wear, when to remove lenses, and other important issues with the participant.

- Participants, who appear unable or unwilling to follow instructions to a degree that, in the Investigator's opinion, jeopardises the participant's wellbeing or the validity of the study, will be discontinued. The reason for discontinuation will be documented.
- The subject will be discharged and asked to return for a follow-up visit (V2) after 1-month.

8.3.3 Visit 3: 2-week follow-up pair 1

The 2-week follow-up visit will be scheduled one month (**14 ± 2 days**) from the initial lens dispensing date. The subject should wear the lenses for a minimum of 2 hours prior to the appointment. If the subject attends without lenses or with less than 2 hours of lens wear on that day and they are not having any problems with their lenses, the visit should be rescheduled, if possible, within the visit window.

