- The following clinical test variables will be recorded on the Follow-Up Visit CRF:

- [Redacted]
- Subjective Assessments
 - [Redacted]
 - Handling (insertion & removal, 0-10 scale)
 - [Redacted]
 - [Redacted]
 - [Redacted]
 - [Redacted]
 - [Redacted]
 - [Redacted]
 - [Redacted]
 - [Redacted]
 - [Redacted]
 - [Redacted]
 - [Redacted]
 - [Redacted]
 - [Redacted]
 - [Redacted]
 - [Redacted]
 - [Redacted]
 - [Redacted]

- [REDACTED]
 - | [REDACTED]
 - | [REDACTED]
- [REDACTED]
 - [REDACTED]
 - [REDACTED]
- [REDACTED]
 - | [REDACTED]
 - | [REDACTED]
 - | [REDACTED]
 - [REDACTED]
 - [REDACTED]
 - [REDACTED]
 - [REDACTED]
 - [REDACTED]
 - [REDACTED]
 - [REDACTED]

[figure not shown]
8.3.4 Visit 4: 1-month follow-up pair 1/dispenses pair 2

The 1-month follow-up visit will be scheduled one month (**28 + 2 days**) from the initial lens dispensing date. The subject should wear the lenses for a minimum of 2 hours prior to the appointment. If the subject attends without lenses or with less than 2 hours of lens wear on that day and they are not having any problems with their lenses, the visit should be rescheduled, if possible, within the visit window.

Visit 4a: Lens evaluation pair 1

- The following clinical test variables will be recorded on the Follow-Up Visit CRF:

- [REDACTED]
 - [REDACTED]
 - [REDACTED]
 - [REDACTED]
 - [REDACTED]
- Subjective Assessments
 - [REDACTED]
 - [REDACTED]
 - Handling (insertion & removal, 0-10 scale)
 - [REDACTED]
 - [REDACTED]

Visit 4b: Dispense pair 2

The study subjects will undergo a trial fit in each eye with the second pair of study lenses.

- The performance of the second pair of study lenses should be assessed after 10-15 minutes settling time and the same variables as those collected on *visit 2* (section 8.3.2) will be assessed.

8.3.5 Visit 5: 2-week follow-up pair 2

The 2-week follow-up visit will be scheduled one month (14 + 2 days) from the initial lens dispensing date. The subject should wear the lenses for a minimum of 2 hours prior to the appointment. If the subject attends without lenses or with less than 2 hours of lens wear on that day and they are not having any problems with their lenses, the visit should be rescheduled, if possible, within the visit window. The same variables as those collected on section 8.3.3 will be assessed at this visit.

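### Does the primary handling comparison lack a visit and a single test, so that its 5% error rate is at risk?

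*Combined protocol and SAP*

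**What the plan says.** Section 2 gives the primary outcome as "Lens handling ratings (ease of insertion & removal. 0 -10 scale". The alternative hypothesis in section 3.1 is "There is a difference between the Avaira Vitality™ toric and Miru 1month toric Menicon lenses in subjective lens handling ratings". Neither names a visit, and nor do sections 10.1 and 10.2.

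Handling is collected more than once per lens. The item "Handling (insertion & removal, 0-10 scale" is listed under Visit 3 (2 weeks, pair 1) and Visit 4 (1 month, pair 1). For pair 2, section 8.3.5 says "The same variables as those collected on section 8.3.3 will be assessed at this visit", and section 8.3.6 likewise carries the Visit 4 variables to Visit 6.

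The time point is stated elsewhere. The Study Design row of the synopsis sets the between-lens comparison "when compared to the Miru 1month Menicon toric lens after 1-month of daily wear". The Purpose row and the aim in section 2 use the same time point. Section 4 describes a one-month cross-over that compares how the two lenses handle.

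On the test, section 10.1 begins by saying that lenses will be compared with paired t-tests. It then lists methods by data type: t-test or analysis of variance for normal data, and Wilcoxon signed-rank for non-normal or ordinal data. Section 10.2 sizes the handling comparison with a paired t-test at alpha 0.05.

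**The concern.** With two rating times per lens and no visit in the hypothesis, a difference seen at only one of them would satisfy the alternative as worded. If the visit could be chosen after seeing the data, the primary result would get two chances at 5%.

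Several loose phrases seem to add doubt about which visit is meant:

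- Section 1 speaks of wearers "refitted with these lenses over 1 month of wear".
- Section 8.3.2 has subjects "asked to return for a follow-up visit (V2) after 1-month".
- Section 8.3.3 states "The 2-week follow-up visit will be scheduled one month", and section 8.3.5 repeats this for pair 2.
- Section 8.3.6 places study completion at Visit 3.

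A 0-10 rating can also be called ordinal, which would send it to Wilcoxon under section 10.1 while section 10.2 plans a t-test. What is at stake is the error rate of the one comparison that the study was sized for.

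**Working it through.** **1. The plan's own figure.** Inputs from section 10.2: alpha 0.05, difference 0.7, SD 1.2 (taken as the SD of the within-subject difference, which the section does not say), 33 completers.

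- Standard error = 1.2/√33 = 0.2089.
- Noncentrality = 0.7/0.2089 = 3.351, with 32 degrees of freedom and a two-sided critical t of 2.037.
- Exact noncentral-t power = 90.1%. With 32 completers it is 89.2%, so 33 is the smallest number that reaches 90%.
- Enrolment: 33 × 1.15 = 37.95, so 38.

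The figure reproduces for one test at the full 5%. Had both visits been meant to count, with alpha split to 0.025 each, power at 33 would be 83.6% and 40 completers would be needed. The sample size is that of a single comparison.

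**2. Which visit?** The relevant places side by side:

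| Place | Time point |
|---|---|
| Synopsis, Study Design and Purpose | 1 month |
| Section 2, aim | 1 month |
| Section 4 | one-month cross-over on handling |
| Outcome line, 3.1, 10.1, 10.2 | silent |
| Any visible text naming 2 weeks as an endpoint | none |

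The only time point attached to the comparison is 1 month, so the comparison is Visit 4 against Visit 6.

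**3. Error rate if either visit were allowed to count.** For two independent tests it is 1 − 0.95² = 9.75%. The between-lens differences at 2 weeks and 1 month come from the same subjects and will be correlated. The documents give no correlation, so a range is assumed, with equal SD at both visits (simulation, n = 33, paired t-test at each visit, 400,000 trials):

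| Correlation | Error rate |
|---|---|
| 0.5 | 9.1% |
| 0.7 | 8.4% |
| 0.9 | 7.1% |

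A separate run of 40,000 trials gave 8.9%, 8.5% and 6.9%. With ratings rounded to whole points and capped at 10 (latent correlation 0.7, latent mean 7 to 9) the rate is 8.6-8.9%. These rates describe a departure from the stated time point. At 1 month alone the rate is 5%.

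**4. Which test?** Simulated whole-point ratings at n = 33, 1 month only, with and without a ceiling at 10 (6,000 trials per setting):

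- No lens difference: t and Wilcoxon disagree in 0.7-0.8% of trials. Taking whichever is significant adds 0.3-0.4 percentage points to the error rate (5.75% to 6.08% without the ceiling, 4.50% to 4.87% with it).
- True difference 0.7: they disagree in 1.5-1.7% of trials. Power is 88.4% (t) against 87.8% (Wilcoxon) without the ceiling, and 85.5% against 85.0% with it.

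Continuous normal differences give larger figures: 5.8-5.9% error if either test may count, and disagreement in about 2% of trials with no difference and about 3% at 0.7. The whole-point figures are closer to what a 0-10 rating yields.

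**5. The visit labels.** The stray one-month wording in 8.3.3 and 8.3.5 sits under headings that say 2-week, next to windows of 14 days. Visits 4 and 6 carry 28 days. The synopsis, the table of contents and section 4 all make Visits 3 and 5 the 2-week visits and Visits 4 and 6 the 1-month visits. The return visit in 8.3.2 and the completion visit in 8.3.6 have wrong visit numbers. None of these moves a rating from one visit to another.

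**The case for a change.** The best case for acting is that the one-month phrase belongs to a general aim covering clinical performance and subjective acceptance, and does not itself define the primary comparison. The hypothesis, read literally, is met by a difference at either visit. A rise from 5% to between 7.1% and 9.1% is a relative increase of roughly 40-80% on the main result, and one sentence would rule it out at no cost in subjects or power.

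Part of this stands. The time point is not carried into the outcome line, section 3.1 or section 10 as they can be read, and a report should say that its primary result is the 1-month comparison.

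The rest does not. The Study Design row applies the time point to the between-lens comparison itself, not only to a general aim. The higher error rates need an analyst to set that aside and claim the primary result from 2 weeks. The visible text is also incomplete: the bullets directly below the primary outcome and the end of section 4 are blacked out and may bear on the 2-week ratings, so their silence cannot be held against the plan. On the test, the opening sentence of 10.1 and the sizing in 10.2 point the same way, and the list by data type is generic across endpoints.

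**Conclusion.** The concern identifies missing detail that an analyst would fill correctly from the synopsis and section 2, together with some clerical slips in visit numbers. It does not show a flaw in the analysis. On the natural reading (one 0-10 handling score, Visit 4 against Visit 6, one paired t-test at two-sided 0.05) the plan delivers its stated 90% power (90.1% recomputed) with 33 completers at a 5% error rate. Writing that reading down would alter no figure.

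The 7-9% error rate is a ceiling under misuse and rests on assumed between-visit correlations of 0.9 to 0.5 with equal SDs. The choice between t-test and Wilcoxon changes the conclusion in under 1% of trials with no lens difference and about 2% at a difference of 0.7. The power figure assumes that the SD of 1.2 refers to the paired difference, which is consistent with 33 reproducing exactly.

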3.1 Study Hypothesis

- Null hypothesis (Ho): There is no difference between the Avaira Vitality™ toric and Miru 1month toric Menicon lenses in subjective lens handling ratings.
- Alternative hypothesis (H1): There is a difference between the Avaira Vitality™ toric and Miru 1month toric Menicon lenses in subjective lens handling ratings.

4 Study Design

This is a 38-subject, prospective, randomized, double masked, (investigator and participant), bilateral, 1 month cross-over study comparing the handling characteristics, (insertion & removal), of asofilcon A toric lenses against fanfilcon A silicone hydrogel toric lenses (table 1). It is anticipated that this study will involve up to 6 scheduled visits: At the first visit, (V1), subject's habitual toric lenses will be evaluated and then re-fitted with both study lenses [REDACTED]. At the second visit, (V2), the first pair of study lenses, (e.g., asofilcon A or fanfilcon A toric lenses), will be dispensed. After 2 -weeks of daily wear, subjects will return for a third evaluation, (V3), and a 4-week visit will be scheduled. At the 4-week visit, (V4), pair 1 will be evaluated and then pair 2 dispensed. Next, a 2-week, (V5), and 4-week visits, (V6) will be scheduled. At visit 6, subjects will exit the study. [REDACTED]

5 Investigational Sites

5.1 Number of Sites

This will be a single center investigational site in Mexico City. (Target 38 subjects).

5.2 Investigator Recruitment

This study will be conducted at the School of Optometry Clinic; National Autonomous University (UNAM) Mexico City. The Investigators will be required to fulfil the following criteria:

- Licensed Optometrist with at least two years of contact lens fitting experience.
- Experienced Investigators who will be trained in Good Clinical Practice (GCP) by the principal investigator.
- In-office email or fax.
- Willingness to follow the study protocol and to co-operate with the study monitors.

This clinical study is designed to be in conformance with the ethical principles in the Declaration of Helsinki, with the ICH guidelines for Good Clinical Practice (GCP) and all the applicable local guidelines.

6 Ethics Review / Statement of Compliance

6.1 Relevant Standards / Guidelines

This implementation document has been developed in accordance with the following:

- ISO 14155 Clinical Investigation of Medical Devices for Human Subjects, Parts 1 & 2, 2011.
- ICH Harmonized Tripartite Guideline for Good Clinical Practice E6, 1996.
- Declaration of Helsinki
- COFEPRIS Applicable Guidelines

6.2 Institutional Review Board

This study will be conducted in accordance with Institutional Review Board regulations (U.S. 21CFR Part 56.103) or applicable IEC regulations. Copies of all IRB/IEC correspondence with the investigator/sponsor will be kept on file. The study will commence upon approval from the following Ethics Committee: Comisión de Ética de la FESI. [name]. [contact] and email address [contact].

6.3 Clinical Trial Registration

This study will be registered with clinicaltrials.gov in accordance with section 801 of the Food and Drug Administration (FDA) Act which mandates the registration of certain clinical trials of drugs and medical devices.

6.4 Informed Consent

Informed consent shall be obtained in writing from the subject and the process shall be documented before any procedure specific to the clinical investigation is carried out.

7 Potential Risks and Benefits to Human Subjects

There may be direct benefits to the subjects in this study such as improved vision, comfort, convenience, and cosmetic advantage. Participation in a study may contribute to scientific research information that may be used in the development of new contact lens products. In addition, subjects will receive an examination of the front part of their eyes and may have the opportunity to try a different type of soft contact lenses and/or different lens care products at no cost to them. The contact lens materials used in this study are commercially available as daily or extended wear. This study will investigate participants' wearing schedule intended for daily wear (NOT extended wear) similar to the average wearing time of 10-16 hours for daily wear lenses.

This study is considered to be a non-significant risk study based on United State Food and Drug administration (FDA) and International Standards Organization (ISO) guidelines because the study devices used as intended in this study (daily wear) don't represent a potential for serious risk to the health, safety or welfare of the subject, and (2) it is not an implant, (3) it is not used to support or sustain human life, (4) it is not of substantial importance in diagnosing, curing, mitigating or treating disease or otherwise prevents impairment of human health, (5) does not present a potential for serious risk to the health, safety or welfare of the subject (Appendix 2).

Complications that may occur during the wearing of contact lenses include discomfort, dryness, aching or itching eyes, excessive tearing, discharge, hyperemia and variable or blurred vision. More serious risks may include photophobia, iritis, corneal edema or eye infection. Although contact lens-related infections are very infrequent, the possibility does exist. The incidence of infection due to day-wear soft lenses is 0.035%. Almost always an infection will occur only in one eye. This risk is assumed by 35-million Americans who currently wear contact lenses.

Routine clinical procedures including auto-refraction, auto-keratometry, visual acuity, anterior ocular health assessment, and contact lens fitting will be used. In addition, high magnification imaging of the lens fit may be made using 35 mm or digital cameras, in vivo confocal microscopy, and/or specular microscopy. Patients will be monitored every two weeks until the end of the study to reduce if not eliminate the occurrence of adverse or potential adverse events. Patients will be given instructions from their ECP regarding early symptoms and signs of adverse events and their contact information.

8 Materials and Methods

